### 10.2. Publication and authorship

The manuscript will be prepared by a writing committee. Prior to publication all hospital leads will be invited to be involved in reviewing drafts of the manuscripts, abstracts, press releases and any other publications arising from the study. All investigators and collaborators in mini-teams including supervising consultant(s) will be acknowledged as PubMed-citable co-authors using a corporate authorship model. Collaborators will have the responsibility of registering this study at their locality, acquiring appropriate approvals, identifying patients, collecting data and completing 30-day follow-up. Where hospital leads fail to submit complete data, or if a hospital's data is removed, collaborators at that hospital will be excluded from the authorship list; if substantially incomplete data is submitted, the writing committee may decide to exclude that unit from further analysis. Authors will acknowledge the study funding sources and other contributors.

**Appendix A (i) - Revised Atlanta Classification of AP severity**

Severity	Definition
Mild acute pancreatitis	Absence of organ failure Absence of local complications
Moderately severe acute pancreatitis	1. Local complications AND/OR 2. Transient organ failure (<48 hours)
Severe acute pancreatitis	1. Persistent organ failure (>48 hours)

**Appendix A (ii) - RIFLE criteria for acute kidney injury/ failure**

Class	Glomerular filtration rate criteria	Urine output criteria
Risk	Serum creatinine x 1.5	< 0.5 ml/kg/hour x 6 hours
Injury	Serum creatinine x 2	< 0.5 ml/kg/hour x 12 hours
Failure	Serum creatinine x 3, or serum creatinine $\geq$ 4 mg/dL with an acute rise >0.5 mg/dL	< 0.3 ml/kg/hour 24 hours, or anuria x 12 hours
Loss	Persistent acute renal failure = complete loss of kidney function > 4 weeks	
End-stage kidney disease	End-stage kidney disease > 3 months	

**Appendix B - Definitions**

Local complication	Definition
Acute pancreatitis (AP)	
The diagnosis of acute pancreatitis requires two of the following three features:
 
 
● Abdominal pain consistent with acute pancreatitis (acute onset of a persistent, severe, epigastric pain often radiating to the back)
 
● Serum lipase activity (or amylase activity) at least three times greater than the upper limit of normal
 
● Characteristic findings of acute pancreatitis on contrast-enhanced computed tomography (CECT) and less commonly magnetic resonance imaging (MRI) or transabdominal ultrasonography (24).
 

Chronic pancreatitis (CP)	
Identification of the following signs via high quality imaging modalities (computed tomography, magnetic resonance imaging):
 
 
● Increased density of the parenchyma
 
● Atrophy of the gland
 
● Calcification
 
● Pseudocysts and irregularities of the main pancreatic duct and its side branches.
 
 
Diagnosis should be based on imaging performed in symptomatic patients presenting with indicators suggestive of pancreatic disease (25).

Specialised pancreas service	Performs elective pancreatic resections
Gallstone (biliary) AP	Confirmation of gallstones using radiological imaging (including abdominal or endoscopic ultrasonography, CT and magnetic resonance cholangiopancreatography)(14,16)
Alcohol induced AP	
History of alcohol consumption (>10g) prior to the diagnosis of acute pancreatitis.
 
10g alcohol is approximately:
 
 
● 300ml beer
 
● 100ml wine
 
● 30ml spirits
 
 
(14,16)

Hypertriglyceridaemia induced AP	
 
● Biliary and alcohol-induced pancreatitis ruled out
 
● Serum triglyceride >1,000 mg/dl ((14).
 

Necrotising AP	
Inflammation associated with pancreatic parenchymal necrosis and/or peripancreatic necrosis, CECT criteria:
 
 
● Lack of pancreatic parenchymal enhancement by intravenous contrast agent and/or
 
● Presence of findings of peripancreatic necrosis (see below—ANC and WON)(24)
 

Interstitial oedematous AP	
Acute inflammation of the pancreatic parenchyma and peripancreatic tissues, but without recognisable tissue necrosis contrast enhanced CT (CECT) criteria
 
 
● Pancreatic parenchyma enhancement by intravenous contrast agent
 
● No findings of peripancreatic necrosis (see above) (24)
 

Acute necrotic collection (ANC)
	
 
● Associated with necrotising pancreatitis (defined above)
 
● Collection containing variables amounts of both fluid and necrosis
 
● Necrosis can involve the pancreatic parenchyma and/or peripancreatic tissues (24).
 

Infected necrosis
	
 
● Pyrexia (>38.0 degrees celsius)
 
● Radiological evidence of infection (presence of gas within the collection seen on CECT) (24).
 

Acute pancreatic fluid collection (APFC)
	
 
● Associated with interstitial oedematous pancreatitis with no associated peripancreatic necrosis.
 
● Areas of peripancreatic fluid seen within the first 4 weeks after onset of interstitial oedematous pancreatitis and without the features of a pseudocyst (24).
 

Enteric fistula
	
Fistulous tract (abnormal connection between two epithelialized surfaces) proven on high quality imaging modalities (CT/MRI), or endoscopic visualisation or intraoperatively (26)

Pancreatic ascites
	
This results from persistent leakage of pancreatic secretions in the peritoneum from pancreatic duct injury. Confirmed with diagnostic paracentesis
 
 
● Amylase level over 1000 IU/L
 
● Protein level greater than 3 g/dL
 
● The calculated serum-ascites albumin gradient (SAAG) is normally less than 1.1 g/dL. This distinguishes from ascites secondary to portal hypertension where amylase levels of ascitic fluid are not elevated, and fluid albumin levels are normally below 1.5 g/dL with a SAAG greater than 1.1 g/dL (27)
 

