## 3. Quality Performance Indicators

Multiple practice guidelines have been published for the management of AP (14–19). The recommendations in these guidelines are usually based on a systematic review of the relevant literature and the evidence on which is based on the available evidence, which is usually graded. Quality performance indicators will be drawn from these evidence-based recommendations for each of the nominated management domains that are relevant to the management of patients within the first 72 hours from admission to hospital. Any differences in the recommendations between the source guidelines will be resolved by discussion amongst the Scientific Advisory Group and consensus established for the QPIs.

The QPIs were developed for the following management domains: (Appendix D: Table 1 with guidelines)

**Table 1.** Quality Performance Indicators

	Domain	QPI	Ref*	Metrics
1	Diagnosis	All patients diagnosed within 12 hours of admission	IAP	RAC criteria for diagnosis: enzymes 3xUL, typical pain ± CT scan
2	Aetiology	All patients had tests for aetiology determined within 24 hours of admission	IAP	U/S for gallstones ETOH history with intake (units per week, timing of binge to pain) If both negative then lipids, IgG4, drugs
3	Severity (predicted)	All patients had prediction of severity on admission	IAP	N / Y, if yes method (drop-down of all options and other) Further drop-down bar will the give options for severity (mild, moderate, and severe)

4	Severity (actual)	All patients had actual severity determined at 48 hours	-	N / Y, if yes method (drop-down RAC, DBC and other) Further drop-down bar will the give options for severity (mild, moderate, and severe)
5	CT scan	Initial CT assessment performed after 72-96 hours if poor response to initial management or clinical deterioration, unless there is diagnostic uncertainty. Not required for severity prediction.	IAP	N / Y, if yes indication (drop-down with other)
6	Transfer	All patients with predicted or actual severe AP in the first 72 hours are discussed with specialist pancreas service.	Nice	N / Y Indication for transfer (drop-down)
7	Analgesia	All patients given narcotic analgesia within one hour of admission	-	Step-up or step-down approach? IV analgesia given on admission N / Y NSAIDS given to mild AP Analgesics prescribed

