## 5.5. Required data

Demographic details	
Age	Year of birth
Sex	Male/ Female/ Other
Ethnicity	European/ Pasifika/ Maori/ Asian/ Middle-Eastern/ Latin American/ African (MELAA)/ other ethnicity
Postcode	
Weight	kg
Height	cm
Smoking history	Current smoker /previous smoker /never smoker e-cigarette /cigarette
Admission details	
Date of first review by doctor/prescriber	Date (dd/mm/yyyy)  *From ED admission note
Time of first review by doctor/prescriber – as per admission note	24 hour clock time
Pancreatic enzymes at admission	Lipase/ Amylase/ Pancreatic amylase (tick one or more and give admission level and indicate what 3x upper limit is
Lipase/ amylase/ pancreatic amylase level	U/L
Epigastric pain confirmed on admission note	Yes/Non-epigastric abdominal pain/ No abdominal pain
Confirmation of AP diagnosis with imaging as per radiological report	MRI/ CT/ Abdominal USS
Charlson Comorbidity Index ( Appendix E )	Score out of 37
Aetiology	
Significant ETOH history investigated in first 72 hours	Yes - from medical history, Yes - ETOH blood test, No

Hypertriglyceridemia investigated in first 72 hours	Yes/No
Acute pancreatitis severity	
Predicted severity on admission as documented in clinical notes (72 hours)	Mild/ moderately severe/ severe
Method used to predict severity	Modified Glasgow/ Ransons'/ BISAP/ APACHE II/ SIRS/ CRP (>150)/ Other (please specify)/ Clinical judgement (no prediction tool)/ No prediction made.
Imaging	
CT assessment performed in the first 72 hours of presentation	Yes/ No
Indication for CT prior to 72 hours	Diagnostic uncertainty/ confirmation of severity based on clinical predictors of severe AP/ Failure to respond to conservative treatment or in the setting of clinical deterioration/ other (please specify)
Imaging of the gallbladder during admission	USS/ CT (gallstones seen on CT)/ MRI/ EUS/ prior imaging confirming gallstones/ previous cholecystectomy/ no imaging
Antibiotics	
Antibiotics administered in first 72 hours of presentation	Yes/ No
Indication for antibiotics	Cholangitis concomitant extrapancreatic infection/ prophylactic/ other – please state
Analgesia	
Simple analgesia (paracetamol/ NSAIDs) prescribed	Paracetamol/ NSAIDs/ Not charted
Simple analgesia frequency	regular/ PRN
Date simple analgesia first administered	Date (dd/mm/yyyy)

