Indication for NBM	for ultrasound scan/ for surgery/ for ERCP/ unknown reason/ other (please specify)
Patient tolerating PO oral intake (clear fluids) by 24 hours	Yes/no
Patient tolerating PO oral intake (clear fluids) by 48 hours	Yes/no
Patient tolerating PO oral intake (clear fluids) by 72 hours	Yes/no
Enteral feeding started in the first 72 hours?	Yes/no
Tolerating enteral feed	Yes/no
Type of Enteral feeding	NJ/NG
Rate of enteral feed	ml/hr
PN in the first 72 hours?	Yes/no
Rate of PN	ml/hr
Anticoagulation	
On regular anticoagulation therapy prior to admission	Warfarin/ dabigatran/ rivaroxaban/ other (please specify)/ Not on regular anticoagulation therapy
Regular anticoagulation continued on admission	Yes/No
(If yes) type of anticoagulation drug	warfarin/ dabigatran/ rivaroxaban/ other
Regular anticoagulation commenced on	Yes - at 24 hours/ Yes - at 48 hours/ No

admission	
Anticoagulation commenced on admission	Prophylactic-dose clexane/ treatment-dose clexane/ anticoagulation not started/ other (please specify)
Local complications in the days prior to the 30-day follow-up	
Necrotising pancreatitis ( Appendix B )	Yes/no
Acute necrotic collections (ANC)	Yes/no
Infected ANC	Yes/no
(If yes) intervention	Endoscopic/ percutaneous/ open necrosectomy
(if yes) date of intervention	Date (dd/mm/yyyy)
Acute pancreatic fluid collection (APFC)	Yes/no
Infected APFC	Yes/no
(if yes) intervention	Endoscopic/ percutaneous/ open necrosectomy
(if yes) date of intervention	Date (dd/mm/yyyy)
Portal/ splenic vein thrombosis	Yes/no
Other local complications	Pleuro-peritoneal fistula/ pleural effusion/ enteric fistula/ gastrointestinal bleeding/ pancreatic ascites/ arterial pseudoaneurysm/ other (free text)
Organ failure and other outcomes during the last 30-days follow-up	
Final aetiology	Alcoholic/ gallstone/ hypertriglyceridaemia/ others
Acute renal failure (as per RIFLE criteria - Appendix A )	Yes/no
Acute renal failure > 48 hours	Yes/no
ICU admission	Yes/no
(If yes) duration of ICU admission	day(s)
New renal dialysis required	Yes/no
(If yes) duration of dialysis	day(s)
New high-flow oxygen/ AIRVO requirement	Yes/no
Duration of high-flow/ AIRVO	days
Noninvasive ventilation required	Yes/no
(If yes) duration of noninvasive ventilation	days
Mechanical ventilation required	Yes/no

(If yes) duration of mechanical ventilation	day(s)
Inotropes required	Yes/no
(If yes) duration of inotropic support	day(s)

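### Appendix B counts any past intake above about one drink as alcohol-induced pancreatitis, which blocks the hypertriglyceridaemia label, leaves drinkers with gallstones uncodable by rule, and gives QPI 2 no usable definition of a negative alcohol history

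*Protocol*

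**What the plan says.** The protocol refers to alcohol as a cause in four places, in different words.

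- **Appendix B, alcohol-induced AP.** The criterion is "History of alcohol consumption", with amount and timing given after a greater-than sign as "10g) prior to the diagnosis of acute pancreatitis". A gloss beginning "10g alcohol is approximately" equates this amount to 300 ml of beer, 100 ml of wine or 30 ml of spirits.
- **Appendix B, hypertriglyceridaemia-induced AP.** Besides triglycerides above 1,000 mg/dl, the definition requires "Biliary and alcohol-induced pancreatitis ruled out". Gallstone AP needs only radiological confirmation of gallstones.
- **Section 3, Table 1, row 2 (QPI 2, aetiology).** The metrics are ultrasound for gallstones and "ETOH history with intake (units per week, timing of binge to pain"), followed by "If both negative then lipids, IgG4, drugs". The row states no cut-off for a negative history and does not refer to Appendix B.
- **Section 5.5, Required data.** The alcohol item is "Significant ETOH history investigated in first 72 hours", answered by method (history, blood test) or no. A separate Yes/No item asks whether hypertriglyceridaemia was investigated. The final aetiology field offers "Alcoholic/ gallstone/ hypertriglyceridaemia/ others", with no ranking and no stated option to choose more than one.

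**The concern.** A definition of a cause normally carries an amount per unit of time, a period before onset, and some way of dealing with competing causes. This one has none of the three. It describes exposure, and the threshold is low enough that light or long-past drinking meets it.

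Two things could suffer. The first is the final aetiology variable. Patients with the same clinical picture may be coded differently between hospitals, in a study with a secondary aim about between-hospital variation. Hypertriglyceridaemia as a cause is also ruled out by definition in anyone above the threshold. The second is QPI 2, one of the twelve domains behind the sole primary outcome in Section 4.1. Its second-line tests are owed only when gallstones and alcohol are both negative, so the meaning of alcohol-negative sets the size of the group in which those tests are judged.

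**Working it through.** **1. The threshold.** Grams = volume (ml) × alcohol by volume × 0.789 g/ml. The strengths and the ethanol density are assumptions, since the protocol gives neither.

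- Beer: 300 × 0.04 to 0.05 × 0.789 = 9.5 to 11.8 g
- Wine: 100 × 0.12 to 0.135 × 0.789 = 9.5 to 10.7 g
- Spirits: 30 × 0.375 to 0.43 × 0.789 = 8.9 to 10.2 g

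The protocol's equivalence is reproduced: 10 g is about one serving.

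**2. The Appendix B definitions as rules.** Let A = ever drank more than 10 g before diagnosis, G = gallstones on imaging, T = triglycerides above 1,000 mg/dl. Then alcohol-induced = A, biliary = G, and hypertriglyceridaemia-induced = T and not G and not A.

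| Patient | Definitions met | Coding of final aetiology |
|---|---|---|
| A only | alcohol | alcohol, however small or remote the intake |
| A and T, no G | alcohol | hypertriglyceridaemia not available, whatever the level |
| A and G | alcohol and biliary | no rule |
| T only | hypertriglyceridaemia | clear |

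The second and third rows follow from the text alone.

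**3. QPI 2 against the data form.**

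- Table 1 names weekly intake and binge timing; Section 5.5 collects neither.
- The Section 5.5 alcohol item records how the history was sought, not what it showed, and leaves *significant* undefined.
- The only alcohol result on the form is therefore the final aetiology field, and Appendix B holds the only stated definition of alcohol-induced AP.
- Section 5.5 lists no IgG4 or drug-review field, so the second-line part of QPI 2 cannot be fully scored from the form under any definition of alcohol.

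**4. Direction, if Appendix B were used as the QPI 2 cut-off.** Among patients without gallstones, let d = share who ever drank more than 10 g and a = share whose AP is truly due to alcohol. The group owed second-line tests is 1 − d under Appendix B and 1 − a under a causal definition. Neither d nor a is in the documents. For assumed d of 0.6 to 0.9 and a of 0.3 to 0.5:

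- Ratio of group sizes, (1 − d)/(1 − a): from 0.1/0.7 = 14% to 0.4/0.5 = 80%.
- Share of alcohol labels that are not causal, (d − a)/d: from 0.1/0.6 = 17% to 0.6/0.9 = 67%.

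For adherence, let f be the fraction of all patients owed second-line tests, and assume first-line work-up is done in 90% and second-line in 40% of those owed it. Adherence = 0.9 × [(1 − f) + 0.4f]. Take 100 patients, 40 with gallstones, 25 with a genuine alcohol cause, and 70% to 85% of the other 60 having ever exceeded 10 g (all assumed):

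- Causal definition: f = (60 − 25)/100 = 0.35, adherence 0.9 × (0.65 + 0.14) = 71%.
- Appendix B, 70%: f = 60 × 0.30/100 = 0.18, adherence 0.9 × (0.82 + 0.072) = 80%.
- Appendix B, 85%: f = 60 × 0.15/100 = 0.09, adherence 0.9 × (0.91 + 0.036) = 85%.

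Upward bias requires only that second-line testing is incomplete and that f is smaller under Appendix B. The sizes come wholly from the assumed inputs.

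**The case against.** The strongest reply is that the protocol never links Appendix B to QPI 2. Table 1 row 2 has its own alcohol metric, and a trivial lifetime intake would not naturally be positive under a weekly-intake measure or under the wording of Section 5.5. The hypertriglyceridaemia item in Section 5.5 also carries no alcohol condition. This stands: the QPI 2 effect is an inference. It does not clear the plan, however. If Appendix B does not govern, the trigger has no cut-off and the form holds no data from which to derive one.

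Three stronger readings are tempting, and the documents do not support them.

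- *Nearly every drinker will be recorded as alcoholic AP.* The final aetiology field does not cite Appendix B, although other Section 5.5 fields do. A drinker with gallstones also meets the biliary definition, and nothing makes alcohol prevail. What can be said is that every such patient meets the alcohol definition.
- *QPI 2 adherence will read 80% to 85% instead of 71%.* Those figures are illustrative. The form cannot fully score the second-line part, so the shift is not shown to occur here.
- *The label cannot be corrected later.* Sections 5.3 and 6.3 have sites keep the key from REDCap ID to hospital number for ten years, so charts can be re-read where intake was noted.

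It is also fair that Section 8 does not name aetiology as an adjustment variable, and that no effect on the overall primary outcome has been shown.

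Leaving the point to an analysis plan would not answer it. The definition is written in the protocol, and a later plan cannot supply intake that the form did not collect.

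**Conclusion.** The concern holds for the definition itself. As written, Appendix B classes anyone who has ever drunk more than about one serving as meeting alcohol-induced AP. It bars those patients from the hypertriglyceridaemia category and leaves drinkers with gallstones under two definitions with no coding rule. These conclusions need no assumption beyond reading the text literally.

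For QPI 2 the conclusion is conditional. The trigger for second-line tests has no stated cut-off. If Appendix B is used as one, the group owed those tests shrinks, and adherence is overstated whenever those tests are incomplete. The documents give no drinking prevalence, no share of alcohol-caused AP and no testing rates, so the size cannot be estimated. The study is not invalidated: the point touches one domain of twelve and one descriptive field. It should still be corrected, because a stated rule misclassifies cause and is cheap to repair.

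**What to change.** - Reconcile the three alcohol wordings (Appendix B, Table 1 row 2, Section 5.5). The Scientific Advisory Group should set one definition with an intake rate and a time window before onset, and say what counts as negative. Use it for the QPI 2 trigger and for the alcohol exclusion in the hypertriglyceridaemia definition.
- Add to Section 5.5 the two items Table 1 already names: weekly intake and the interval from binge to pain.
- Add Yes/No items for IgG4 and drug review, so that the second-line part of QPI 2 can be scored.
- State a hierarchy for final aetiology, or allow more than one cause to be recorded.

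The cost is one revised definition, a few REDCap items and one coding rule. Intake will be missing from some notes, and that should be recorded as unknown, not as negative. If data entry has already closed, the same items can be sought by chart re-review through the sites' key, where intake was documented.

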### 4.2. Secondary outcomes

- Variation in compliance with QPIs between hospitals for each of the management domains
- Requirement for mechanical ventilation (invasive and non-invasive)
- Requirement for renal replacement therapy
- Requirement for inotropic or vasopressor support
- Intervention for a complication of AP
- Alive and discharged at 30-days

[figure not shown]

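### Infected necrosis is defined by fever and gas on CT with no combining rule and no culture criterion, infected APFC has no definition, and the form records an intervention only after infection is coded Yes

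*Protocol*

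**What the plan says.** The entry for infected necrosis in Appendix B has two bullets and nothing else: pyrexia above "38.0 degrees celsius", and "Radiological evidence of infection (presence of gas within the collection seen on CECT". No word joins them, and no aspirate, drain or operative culture is mentioned.

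Other entries in the same appendix do state their rule. For acute pancreatitis it is "The diagnosis of acute pancreatitis requires two of the following three features". For necrotising disease the first criterion reads "Lack of pancreatic parenchymal enhancement by intravenous contrast agent and/or", so either is enough.

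In section 5.5 (local complications), infected ANC is a yes/no row. It is followed by two conditional rows, the type of intervention ("Endoscopic/ percutaneous/ open necrosectomy") and its date. The same block is repeated under "Infected APFC". Section 4.2 lists "Intervention for a complication of AP" as a secondary outcome, with no restriction to infected collections.

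**The concern.** Infection status is abstracted from charts by local teams that include medical students and junior doctors (section 5.2), with up to eight collectors per hospital (section 9). The protocol describes no central adjudication of infection, so the definitions table is what has to keep coding consistent between sites. A definition that can be read in two ways, with a further case (positive culture) that neither reading covers, does not do that.

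The consequence goes beyond the infection variable. The intervention rows hang on the infection answer, so the reading also decides which drainages and necrosectomies enter a secondary outcome. Section 8 plans models comparing clinical outcomes between patients managed according to the quality indicators and those who were not, and funnel plots by hospital for some secondary outcomes. A difference between sites in reading two bullets could then appear as a difference in outcome. An intervention that was never entered cannot be restored by any later analysis choice; only a return to the chart would recover it.

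**Working it through.** The protocol states no event count, sample size or misclassification rate on this point, so there is no figure to reproduce. The first three steps are logic. The fourth is illustration on assumed rates.

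**1. What each reading does to an ANC**

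| Fever | Gas on CECT | Both needed | Either enough |
|---|---|---|---|
| yes | yes | Yes | Yes |
| no | yes | No | Yes |
| yes | no | No | Yes |
| no | no | No | No |

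A positive culture changes no cell. If both signs are needed, a culture-proven collection without gas is coded No, and so is one with gas in an afebrile patient. If either is enough, every febrile patient with an ANC is coded Yes, although section 1 describes the disease itself as involving a systemic inflammatory response.

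**2. Infected APFC.** Appendix B has no entry for it. The infected necrosis entry cannot be borrowed, because the APFC entry requires that peripancreatic necrosis be absent.

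**3. The form.** Elsewhere in section 5.5 a conditional row depends on the row above it (ICU stay, dialysis, ventilation). Read the same way, the intervention rows open only on Yes to infected ANC or infected APFC. No other row records an intervention on a pancreatic collection; the transfer block mentions one only as a reason for transfer. Bleeding, pseudoaneurysm and fistula are listed with no intervention row. An intervention on a collection coded No therefore has no place on the form, while the outcome in section 4.2 would count it.

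**4. Size, on assumed rates.** Let f be the probability of fever and g the probability of visible gas in a truly infected collection, taken as independent. The protocol gives neither.

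- Both needed: share of infected collections coded No = 1 − f·g. With f from 0.5 to 1.0, this is 80–90% at g = 0.2, 60–80% at 0.4, 50–75% at 0.5, 40–70% at 0.6, 20–60% at 0.8 and 0–50% at 1.0.
- Either enough: share coded No = (1 − f)(1 − g). With f from 0.5 to 1.0 and g from 0.2 to 0.8, this is 0–40%.

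Independence matters. At f = 0.8 and g = 0.5, the share detected when both are needed is 0.8 × 0.5 = 0.40. With strong positive dependence it could reach min(f, g) = 0.50.

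Take 100 ANC, with 30 assumed infected, f = 0.8, g = 0.5, no gas in sterile collections, and fever in 20–50% of the 70 sterile ones.

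- Both needed: 30 × 0.8 × 0.5 = 12 coded infected.
- Either enough: 30 × (1 − 0.2 × 0.5) = 27 true, plus 70 × 0.2 = 14 to 70 × 0.5 = 35 false, giving 41 to 62.

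Varying the infected share over 0.2–0.4 and g over 0.2–0.8, with f kept at 0.8 and the same sterile fever range, the ratio between the two readings runs from 50.4/25.6 ≈ 2 to 56.8/3.2 ≈ 18.

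**The case against.** The strongest reply is that the text leans one way. Several neighbouring lists without a connector (interstitial oedematous disease, ANC, APFC, hypertriglyceridaemia) make sense only as cumulative, and where alternatives are meant the appendix says so. That makes the both-needed reading the likelier one. The chronic pancreatitis list leaves its rule open, however, so the convention is not secure. The likelier reading is also the one that codes a culture-proven collection without gas as uninfected.

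The link from form to definition is inferred. The pointer to Appendix B sits on the necrotising pancreatitis row, and the form says infected ANC where the appendix says infected necrosis. This stands as a caveat, but the protocol offers collectors no other definition.

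It is also true that the unrecorded interventions come mainly from the form's branching. Drainage of an uninfected collection would be lost under a perfect definition. This widens the fix and does not remove the point.

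Two stronger readings are tempting and should be resisted. A reader might infer that most infected collections will be coded No. That needs the both-needed reading and f·g below 0.5, and the protocol gives no basis for either rate. A reader might also infer, from the row "Simple analgesia (paracetamol/ NSAIDs) prescribed", that paracetamol will mask fever and so hide infection. That row records prescribing in the analgesia block, and nothing links it to temperature when a collection is assessed.

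Finally, the reach is limited. Compliance with the quality indicators, the primary outcome, does not use infection, and neither does the severity classification in Appendix A. Section 8 does not name this outcome for the funnel plots.

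**Conclusion.** The point holds as a fault in data definition and form design. As printed, infection coding depends on the collector's reading, culture-proven infection has no route to Yes in its own right, infected APFC cannot be coded to any definition, and interventions on collections coded No are missing from an outcome that should include them. These conclusions need no assumed rates. They rest on two readings of the protocol: that the infected necrosis entry governs the infected ANC row, and that the conditional rows depend on the row above.

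The amount of misclassification cannot be derived from the protocol. The illustration shows only that the two readings can differ by a factor of about 2 to 18 under the assumed rates. The damage is confined to the infection variables and one secondary outcome. It should be corrected, but it does not threaten the primary result.

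**What to change.** All three changes concern data coding only and leave care untouched.

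1. In Appendix B, state one rule for an infected collection that covers both ANC and APFC, accepts a positive culture from a sample taken in routine care, and does not let fever alone decide.
2. Add a field recording the basis for a Yes: gas, culture, or both.
3. Ask about intervention and its date for every local complication, independently of the infection answer. Without this, the first two changes leave the intervention gap open.

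The cost is a short rewrite of one definition and one or two extra fields filled from the existing chart. If entry has already closed, the key linking REDCap numbers to patients that each hospital keeps (section 5.3) would allow a targeted return to the charts of patients with a recorded local complication.
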